The Corindus CorPath GRX Neuro trial is a prospective, single-arm, international, multi-center, non-inferiority study to evaluate the effectiveness and safety of the CorPath GRX System for endovascular cerebral aneurysm embolization compared to historical controls. Subject selection requires a clinical indication for endovascular coil and/or stent-assist coiling embolization of cerebral aneurysms.

The CorPath GRX System is intended for use in the remote delivery and manipulation of interventional devices during percutaneous coronary and vascular procedures. The CorPath GRX System is designed to allow the operator to remotely manipulate interventional devices within a patient's vasculature to perform vascular procedures in a precise and well-controlled fashion, without being exposed to radiation levels typically encountered during a conventional (i.e., manual) procedure. The complete CorPath GRX System includes a bedside unit, interventional cockpit, and control console.

The recruitment phase is 18 months, follow-up is 180 days, and total study duration is 24 months. All subjects will be followed post-CorPath GRX endovascular embolization procedure through 180 days.

The subject population is subjects with a clinical indication for endovascular coil and/or stent-assisted coiling embolization of cerebral aneurysms. Up to 120 subjects will be enrolled in order to achieve at least 108 subjects in the study; each site will try to recruit a maximum of 20 subjects.

The data collection schedule is provided in Table 1 below.

Table 1. Data collection schedule

	Pre-procedure	Procedure	Post Procedure
			(24 hours post-procedure or hospital discharge)
Patient Eligibility Criteria	X		
Medical History	X ¹		
Head CT angiography or MRI angiography	X ¹		
Clinical assessment & Physical exam: including: 
• Hunt and Hess scale• Modified Rankin score• Raymond Grade for previously coiled aneurysms• National Institutes of Health Stroke Scale (NIHSS) scale• World Federation of Neurological Surgeons (WFNS) Subarachnoid Hemorrhage (SAH) Grade• Fisher grade	X ¹		X
Raymond Grade-Roy Occlusion Classification Scale	X ³		X
Laboratory Tests: complete blood count, hemoglobin, platelet count, platelet function testing, pregnancy test, serum creatinine and glomerular filtration rate.	X ^{1,2,4}		X ²
Procedure Parameters (CorPath GRX use, procedure time, fluoroscopy time, patient radiation exposure, etc.)		X	
Angiography		X ⁵	
Contrast volume		X	
Record of AEs		X	X
Data for aneurysm assessment		X	X

¹ Within 7 days of index procedure.

² If performed under standard hospital procedure.

³ For previously coiled aneurysms.

⁴ Female subjects of child-bearing potential must have negative pregnancy test (urine or serum).

⁵ Includes angiograms in the anterior posterior, lateral and working positions for analysis by a core laboratory.

3 Sample Size

3.1 Determination of Historical Control

Safety rates from key literature are presented in Table 2 below:

Table 2. Rates of safety from literature for endovascular treatment of unruptured and ruptured aneurysms.

	N Aneurysms (Pts)	Mortality at Discharge	Overall Complication Rate	Rupture/ perforation Rate (%)	Embolism Rate (%)
UNRUPTURED INTRACRANIAL ANEURYSMS					
Algra et al 2018*	73066 (71819)	0.3% (0.2% - 0.4%)	4.96% (4.00, 6.12%)	0.9% (212/18520) 95% CI (0.6%, 1.3%)	2.82% (437/16000) 95% CI (2.3, 3.5%)
Advanced Endovascular Methods**	2248	0.4% (0.2 - 1.1%)	6.1% (4.3, 8.7%)		
Kawabata et al 2017	1406 (1375)			1.4% (20/1406)	
coil only	340			1.8% (6/340)	
stent-assisted coiling	468			0.9% (4/468)	
balloon-assisted coiling	598			1.7% (10/598)	
From Lit Review, Table 6 in Kawabata	7785	0		1.4% (108/7785)	
Zheng et al 2016	1127			1% (11/1127)	
Santillan et al 2013	217	0%		5% (3/217)	
Shigematsu et al 2013	4767			1.4% (65/4767)	
Oishi et al 2012	500	0%		1.4% (7/500)	
Im et al 2009	435	0%		0.9% (4/435)	
Pierot et al 2008	739	0.3%		2.4% (18/739)	
Pierot et al 2008 (ATENA study)	739 (649) (700 procs)	1 month 1.4%	15.4%	2.4% (18/739) 2.6% (18/700)	7.3% (29/308) 7.1% (per proc)
Pierot et al 2009, (ATENA study, coil alone results)	325 pts	0.9% (3/325)	10.8% (35/325)	2.1% (7/325)	6.2% (20/325)
RUPTURED INTRACRANIAL ANEURYSMS					

	N Aneurysms (Pts)	Mortality at Discharge	Overall Complication Rate	Rupture/ perforation Rate (%)	Embolism Rate (%)
Zhang et al 2019	1004	All cause 9.5% (5.8%, 13.2%) proc related 1.8% (0.9, 2.7%)	22.7%*** 95% CI (15.1, 30.3%)		
Cognard et al 2011 (CLARITY GDC study)	405	1.50%		3.7% (15/405)	13.3% (54/405)
Pierot et al 2011 (CLARITY)	608	5.1% (31/608) cum. TRT related morb/mort rate 19.6% (119/608) cum. morb/mort rate)	17.4% (106/608)	4.6 (28/608)	

* rates presented are pooled crude risk from meta-analysis modeling

** Advanced = Stent-assisted coiling, balloon-assisted coiling, flow diverting stents or woven endobridge devices.

*** definition not specified

Additionally, there were three randomized controlled trials comparing different endovascular treatments that contained both ruptured and unruptured intracranial aneurysms: HELPS, MAPS, and Cerecyte Coil trial. Rates presented pooled results from both arms in the following three tables.

Table 3a-3c. Rates presented pooled results from both arms from three (3) from randomized control trials.

HELPS Trial	N	Mortality	Procedural aneurysm rupture*	Thromboembolic complication*
White et al 2008 N=499 RCT, covered vs uncovered coil 53% ruptured	499	2.2% (11/499) At discharge	3.4% (17/499)	9.8% (39/499)

* Article specifically called out that “some of these adverse events, especially procedural ones, did not result in permanent clinical sequelae.

MAPS Study	N	Mortality	Overall Complication Rate	Clinical Event Committee Adjudicated			Technical Success
				Rupture/re-rupture	Ischemic Stroke	Hemorrhagic Stroke*	
McDougall et al 2014 N=626 RCT, Matrix coil vs GDC coil Ruptured 36.4% (228/626)	626	0.2% (1/624) Peri-proc 2.4% (15/626) 30 day	14.9% (93/624)	0.3% (2/626)	3.4% (21/626)	1.1% (7/626)	97.1% (608/626)

*Article notes hemorrhagic strokes due to rupture/re-rupture are not included in Hemorrhagic Stroke summary

CERECYTE Coil Trial	N	Mortality	Overall Complication Rate	Rupture/re-rupture	Thrombo-embolic complication	Neuro-deterioration	Technical Success
Coley et al 2012 N=500 RCT, Cerecyte vs bare platinum coil Ruptured 46.9% (233/497)	497	0% within 24-hr 0.4% (2/497) before discharge	12.3% (61/497)	3.6% (18/497)	5.6% (28/497)	3.0% (15/497)	97.2% (483/497) (14 "unable to place coil")

While Cerecyte and HELPS present overall complication rates in the 12-15% range, it was felt that the rates of stroke, rupture/re-rupture and death from the MAPS trial that were adjudicated by an independent clinical event committee were the most accurate to represent the expected rates of safety events for this trial. If we assume independence and add the individual rates, the expected rate of safety events is 4.8% (30/626) but will be rounded to the nearest percent of 5% for sample size calculations.

The performance endpoint is similar to a technical success measure. Zang et al 2019 provided a literature review that included technical success. The weighted average was 97.6% for ruptured aneurysms. McDougall et al 2014 reported a similar overall procedural success of 97.1% (608/626) and Coley et al 2012 report a success of 92.7%, but this number does not include conversion to manual as our performance endpoint does.

For the conversion to manual aspect, there are not data available for treatment of intracranial aneurysms, but we can look at past Corindus CorPath performance for PCI. In Table 4 below, the premarket trial results 1.2% for unplanned conversions, but the rate was considerably higher in the real world post-market trial with 10.4% unplanned conversions.

To estimate the overall rate of success for the performance endpoint, we will use the highest rate of 10.4% rounded to the nearest percent of 10%, or in terms of success, 90% expected performance success rate.

Table 4. Summary of conversion to manual by Corindus CorPath device in percutaneous coronary interventions.

Trial		Conversion to Manual
PRECISE	Pre-market trial for FDA clearance	1.2% (2/164)
PRECISION Registry*	Post-market trial	10.4% (99/948)
CORA-PCI	Post-market single site trial	8.3% (9/108)
* Unpublished data		

3.2 Sample Size Calculation

The goal of the primary analysis will be to demonstrate that cerebral aneurysm coiling treated with CorPath GRX is as effective and safe as compared to the combined historical control treatments for cerebral aneurysm coiling treated with traditional manual operation.

For safety, if the upper bound of the 2-sided 95% confidence interval is less than the performance goal of 15%, we will conclude that the Corindus GRX system did not negatively impact safety.

For performance, if the lower bound of the 95% confidence interval for the proportion of successful patients is greater than the performance goal of 80%, we will conclude that the Corindus GRX system did not negatively impact performance.

Assuming that the expected safety for procedures performed with the Corindus GRX system do not differ from historical performance, we set up a performance goal using the historical rate of 5% for safety and an 10% non-inferiority margin to set up a performance goal of 15% for safety.

The safety hypothesis is:

$$H_0: p \geq 15\% \text{ (5\% + 10\% NI margin)}$$

$$H_a: p < 15\%,$$

where p =proportion of patients with a safety event.

A sample size of 96 subjects will have at least 90% power to test this safety hypothesis (PASS 14, one-sample proportion, exact test, normal approximation for power).

Assuming that the expected procedure success rate is similar to the 90% based on literature and our best estimate of possible conversion to manual procedures, we set up a performance goal using the historical rate of 90% for with a 10% non-inferiority margin to set up a goal of 80% for performance.

The safety hypothesis is:

$$H_0: p \leq 80\% \text{ (90\% - 10\% NI margin)}$$

$H_a: p > 80\%,$

where p =proportion of patients with a successfully completed endovascular procedure.

A sample size of 108 subjects will have at least 80% power to test this safety hypothesis (PASS 14, one-sample proportion, exact test, normal approximation for power).

The overall trial sample size for the trial will be driven by the performance endpoint with at least 108 subjects enrolled.

4 Statistical Analyses and Study Objectives

All statistical analyses will be performed using SAS Version 9.4 or higher or other valid statistical software. Descriptive summary statistics will be provided for endpoints along with 95% confidence intervals as appropriate. Subject data listings and tabular and graphical presentations (e.g., bar graphs, pie charts, line graphs) of results may also be provided.

The primary objective of this study is to evaluate the effectiveness and safety of robotic-assisted endovascular embolization procedures compared to objective performance criteria based on the scientific literature.

4.1 Definition of Analysis Populations

Analysis Cohort: Any subject with an attempted endovascular procedure (a non-missing robotic microcatheter insertion time).

Per-Protocol Cohort: Any subject in the analysis cohort who did not have a major protocol deviation.

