#### CorPath Use Technique

*To obtain proper data for analysis, the following procedure, with associated data collection milestones, is recommended, but in no case, dictates use of the CorPath GRX System in a manner*

*Version Date: May 21, 2021*

*This confidential document is the property of Corindus, Inc. and shall not be reproduced, distributed, disclosed or used without the express written consent of Corindus, Inc.*

*different from that presented in the Operator's Manual.*

**The following CorPath Use Technique guides the Investigator through coiling a cerebral aneurysm with the CorPath GRX System.**

1. Obtain arterial access using conventional technique. Record sheath insertion time.
2. Once arterial access is obtained, insert a standard diagnostic catheter using conventional manual technique or guide catheter mounted coaxially over a diagnostic insert catheter.
3. Manually advance the diagnostic select catheter to the parent vessel.
4. Advance guide catheter to desired location in parent vessel and remove wire and diagnostic select catheter. If only diagnostic catheter was used, then remove standard wire and use exchange length guidewire; remove the diagnostic catheter over the exchange wire while maintaining distal wire position. Advance the guide catheter over the exchange wire to the desired location in parent vessel and remove wire.
5. The Investigator will specify which devices will be delivered robotically.
6. Manually advance microcatheter to tip of guide catheter in the parent vessel.
7. Manually insert exchange length guidewire and attach COPILOT bleed back control valve to the microcatheter.
8. Record microcatheter "insertion" time.
9. Load the microcatheter and exchange length guidewire in the CorPath GRX cassette.
10. Using the CorPath System, advance guidewire and microcatheter independently to target treatment area. The Active Device Fixation (ADF) technIQ automated movement can be enabled to keep the guidewire in place during microcatheter movement.
11. With microcatheter in place, remove guidewire.
12. Advance stent into the COPILOT bleed back control valve and proximal microcatheter slowly and according to stent delivery IFU.
13. Place the stent advancement wire into the Device Track of the CorPath GRX.
14. Advance stent, robotically, to target area. The stent will remain completely sheathed in the microcatheter.
15. Robotically position the stent across target aneurysm.

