#### **4.8.6 Specify Device to Be Used Robotically**

After arterial access prior to using the CorPath GRX System, the Investigator will specify which device he/she will plan to use robotically. If a device that is used robotically cannot be delivered to the target, cross the target or delivered into the target and conversion to manual is needed, it will be documented as an unplanned conversion to manual.

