#### **4.8.7 Conversion to Manual Procedure Data Collection**

The Investigator shall determine if it is necessary to convert to standard manual techniques to complete the endovascular robotic procedure. The Investigator should make this decision based on his/her medical assessment of the situation in accordance with the best interest of the subject. It is recommended that conversion to manual operation be performed at the discretion of the Investigator or if any of the following occur:

- The inability to navigate the guidewire(s), microcatheter(s), embolization coil(s) or stent-assist coiling using the CorPath GRX System as intended.
- Any clinical condition that requires rapid medical intervention. Details of manual technique to be documented are:
  - Planned or unplanned (e.g. physician preference, use of equipment not compatible with CorPath GRX);
  - If unplanned (e.g. embolization coils were undeliverable due to severe tortuosity), specify why.

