## 6. STATISTICAL CONSIDERATIONS AND ANALYSIS

Data for subjects that undergo an endovascular procedure where the Corindus GRX device is used (or attempted to be used) will be included in both primary and secondary endpoints where data are available.

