4.2 Primary Effectiveness Endpoint

Objective: To assess effectiveness of using CorPath GRX for robotic-assisted endovascular procedure.

Hypothesis:

$H_0: p \leq 80\% \text{ (90\% - 10\% NI margin)}$

$H_a: p > 80\%,$

where p =proportion of patients with a successfully completed endovascular procedure.

Endpoint: The proportion of subjects with successful completion of the robotic-assisted endovascular procedure absent any unplanned conversion to manual for guidewire or microcatheter navigation, embolization coil(s) or intracranial stent(s) deployment, or an inability to navigate vessel anatomy.

Subjects to Include: Analysis Cohort

Statistical Analysis: The proportion of subjects with a successful procedure completion as defined will be summarized along with a 2-sided Clopper Pearson Exact 95% confidence interval. If the lower bound is greater than 80%, we will declare success and conclude that effectiveness is not inferior to the performance goal of 80%.

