4.3 Primary Safety Endpoint

Objective: To assess safety of using CorPath GRX for robotic-assisted endovascular procedure.

Hypothesis:

$H_0: p \geq 15\% (5\% + 10\% \text{ NI margin})$

$H_a: p < 15\%,$

where p =proportion of patients with a safety event.

Endpoint: The proportion of subjects with a safety event where a safety event is intra- and peri-procedural events, including target aneurysmal rupture, vessel perforation or dissection, and thromboembolic event with neurological decline within 24 hours post-procedure or hospital discharge, whichever occurs first.

Subjects to Include: Analysis Cohort

Statistical Analysis: The proportion of subjects with a safety event as defined will be summarized along with a 2-sided Clopper Pearson Exact 95% confidence interval. If the upper bound is less than 15%, we will declare success and conclude that safety is not worse than the performance goal of 15%.

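### SAP 4.1 lets an undefined robotic timestamp decide who enters both primary analyses, whereas Protocol 6 takes in every attempted use of the device

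*SAP*

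**What the plan says.** SAP 4.1 defines the Analysis Cohort as "Any subject with an attempted endovascular procedure (a non-missing robotic microcatheter insertion time"). SAP 4.2 (effectiveness) and SAP 4.3 (safety) both use it; the latter reads "Subjects to Include: Analysis Cohort". One field therefore sets both primary denominators.

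Protocol 6 sets no time condition. It says that subjects "where the Corindus GRX device is used (or attempted to be used) will be included in both primary and secondary endpoints where data are available".

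The nearest named item is step 8 of the CorPath Use Technique in Protocol 4.8.5: "Record microcatheter 'insertion' time". It comes after the microcatheter has been advanced by hand (step 6) and before step 9, "Load the microcatheter and exchange length guidewire in the CorPath GRX cassette". Robotic movement starts at step 10. SAP 4.4.6 starts the robotic procedure time at a different point, the first device used robotically.

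SAP 4.2 requires successful completion "absent any unplanned conversion to manual for guidewire or microcatheter navigation". SAP 5 assumes that the primary data will be complete, and gives no rule for a blank time.

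**The concern.** In a single-arm trial judged on two proportions, who is in the denominator matters as much as who has the event. The two documents describe the same idea, an attempted procedure, but the SAP turns it into the presence of a timestamp whose meaning is not fixed. The step 8 time is not robotic, so the SAP's adjective does not match the only insertion time in the workflow. The case report form that could settle this is not among the documents.

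If the field is a robotic-phase time, an attempt abandoned before that moment has no time and leaves the analysis. It did not complete robotically, so SAP 4.2 would score it as a failure. Each such loss favours the device on effectiveness. The words in Protocol 6 about available data do not excuse the loss, because the outcome is known and only a timestamp is absent.

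For safety the direction depends on who is lost. Dropping a subject with an event favours the device; dropping an event-free subject goes slightly against it.

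**Working it through.** **Inputs.** From SAP 3.2, 4.2 and 4.3: goals of 80% (effectiveness) and 15% (safety); expected rates of 90% and 5%; two-sided 95% Clopper-Pearson limits, so one-sided 2.5%; 108 subjects, with up to 120 enrolled. The number of untimed attempts is given nowhere and is an assumption throughout.

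**The plan's own figures.** n = [(z₀.₉₇₅√(p₀q₀) + z_power√(p₁q₁)) / (p₁ − p₀)]².
- Effectiveness: p₀ = 0.80, p₁ = 0.90, 80% power gives 107.4, so 108.
- Safety: p₀ = 0.15, p₁ = 0.05, 90% power gives 95.9, so 96.

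Both figures reproduce. The sample size is not in dispute; the point is who is counted.

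**What each reading keeps.**

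| Reading of the SAP field | Kept | Lost | Wrongly admitted |
|---|---|---|---|
| Step 8 time | Every attempt that follows the workflow as far as the cassette | Set-up failures before step 8; blanks | A subject timed at step 8 whose robot was never loaded |
| Later robotic-phase time | Attempts that reach that time, including later conversions | Attempts abandoned before it, for example at cassette loading or from early device failure; blanks | None evident |

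Guidewire-navigation failures need care. Steps 9 and 10 load the guidewire and microcatheter together and then advance both. Such a failure is lost only if the time is taken after the guidewire has been navigated. If it is taken at loading or at the start of robotic movement, the failure is timed and counted.

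**Effectiveness, k failures dropped from 108 attempts.** Success needs a Clopper-Pearson lower limit above 80%.
- All counted: at least 95/108 (lower limit 80.3%). 94/108 fails (79.2%).
- One failure dropped: 94/107 passes (80.1%).
- Minimum successes: 95 (n = 108), 94 (107), 94 (106), 93 (105).
- With X ~ Bin(108, 0.80): P(X ≥ 95) = 2.1% for k = 0; P(X ≥ 94) = 3.9% for k = 1 or 2; P(X ≥ 93) = 6.7% for k = 3.
- With 120 attempts the minimum successes are 105, 104, 104 and 103 for k = 0 to 3, and the probabilities are 2.2%, 3.9%, 3.9% and 6.5%.

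**A version not tied to a fixed k.** Let each failure be untimed with probability q and sum over s successes and d dropped failures: P = Σ Bin(s; 108, 0.80) · Bin(d; 108 − s, q) · 1[lower limit of s/(108 − d) > 0.80]. The expected number dropped is 108 × 0.20 × q.

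| q | Expected dropped | P(declare success) |
|---|---|---|
| 0 | 0 | 2.1% |
| 5% | 1.1 | 3.1% |
| 10% | 2.2 | 4.4% |
| 20% | 4.3 | 10.1% |

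**Safety.** The upper limit must be below 15%.
- 9/108 fails (15.2%). Losing one event gives 8/107, which passes (14.2%).
- At a true 15% with 108 attempts, P(declare safe) is P(X ≤ 8) = 1.3% with none dropped, P(X ≤ 9) = 2.9% with one event dropped and P(X ≤ 10) = 5.6% with two.
- In the other direction, losing three event-free subjects moves 8/108 (14.07%) to 8/105 (14.46%). From 120 attempts, losing two event-free subjects lowers the maximum permitted events from 10 to 9, and P(declare safe) falls from 2.2% to 1.0%.

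**The case against.** The ordinary reading is step 8. It is the only insertion time in the workflow, it pairs with the removal time at step 26, and it precedes cassette loading, so almost nothing is lost. SAP 4.1 also opens with the same idea of an attempt as Protocol 6, and the bracket may be no more than an operational flag. This stands as a reason to expect a small effect. It does not settle the matter, because the SAP calls the time robotic and step 8 is not. Even on this reading the cohort differs from Protocol 6 at both edges.

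Safeguards exist. Investigators sign off after queries are resolved (Protocol 7.1), source verification is 100% (8.1, 8.2), all malfunctions are recorded (4.8.8), and the SAP summarises malfunctions and deviations (4.5). These make accidental blanks unlikely and abandoned attempts visible. They cannot supply a time for a step never reached, and they do not restore a subject to the denominator.

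A reader might infer that the rule removes guidewire-navigation failures in general, since Protocol 4.8.7 lists "The inability to navigate the guidewire(s), microcatheter(s), embolization coil(s) or stent-assist coiling using the CorPath GRX System as intended" as a ground for conversion and 4.8.6 says that if "conversion to manual is needed, it will be documented as an unplanned conversion to manual". The documents do not support that: the loss arises only if the time follows guidewire navigation. Section 4.8.6 also speaks of a device already in robotic use, so it does not describe set-up failures.

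A reader might also infer that nothing separates an abandoned attempt from a screen failure (Protocol 4.5). That goes too far, because Protocol 6 places attempted use in the analysis. What is missing is a recorded event that marks where an attempt begins.

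Finally, events in subjects lost before the robotic phase are likely to be few. Protocol 3.3 limits vascular injury to that caused by robotically controlled devices. SAP 4.3 omits this limit, and thromboembolic events remain possible.

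**Conclusion.** The point holds in a conditional form. SAP 4.1 makes both primary denominators depend on a field that the documents do not define, and its rule can be narrower than Protocol 6. On the step 8 reading the effect is small. On a later-time reading, known effectiveness failures leave the analysis, and the bias favours the device.

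The size is hypothetical. The error rates assume a true success rate of exactly 80%, which is where the false-positive rate is defined but lies below the planned 90%. They also assume one to three dropped failures, or a stated untimed share. The 10.1% figure needs one failure in five to be untimed and should not be read as a forecast. What the figures do show is that one dropped failure can reverse a borderline result and take the error rate above the nominal 2.5%.

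The safety effect can go either way and is probably small. It would be wrong to conclude that the plan does exclude failures; the documents show only that the rule permits it.

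**What to change.** In SAP 4.1:
- define the Analysis Cohort as every subject in whom use of CorPath GRX was begun or attempted, in line with Protocol 6;
- name the recorded event that starts an attempt, so that it is distinct from a screen failure under Protocol 4.5 (for example, first device loaded in the cassette, or an earlier set-up failure of the system after devices have been declared under 4.8.6);
- state that a missing time never excludes an attempted case;
- count an abandoned attempt as an effectiveness failure and include its safety events;
- list every subject with devices declared under 4.8.6 who falls outside the cohort, with the reason.

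If step 8 was intended, saying so resolves most of the ambiguity, but the rule on missing times and the start event are still needed.

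The cost is a few sentences and one listing, with no new patients, visits or tests. The downside is that abandoned attempts count against the device, and the start event must be fixed before the data are seen.
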